7.4.4.6 Pulse Oximetry and ECG Monitoring

Continuous pulse oximetry and ECG monitoring will be performed starting 30 min prior and continuing through 30 minutes following IP administration for all subjects suffering from pulmonary hypertension or unstable cardiopulmonary conditions.

7.4.4.7 Sedation

When children are unable to cooperate, sedation may become necessary to ensure that images of diagnostic quality are obtained. Whether or not sedation is necessary depends on several variables, including age and maturity of the subject, prior sedation history, duration of the procedure, and any associated discomfort. Subjects will be sedated or anesthetized only for

procedural purposes and then according to standard hospital routines by qualified individuals (e.g., nurses, physicians, or physician assistants) who are experienced in the management of sedated children and have the knowledge to perform careful subject screening so as not to put any subject at unacceptable risk of serious complications.

All drugs administered for sedation will be recorded on the Case Report Form on the Concomitant Medications page. Monitoring of the subject will start with documentation of pre-sedation vital signs, and ECG recordings on the Case Report Form. Continuous subject monitoring should be conducted according to routine clinical practice. When sedation is required, additional vital signs and ECG data will be performed after sedation and before the echocardiography examination and recorded on the CRF.

Whenever adverse events are recorded, the Investigators will be asked to prospectively report in the CRF their causality assessment including an evaluation of whether the event may be related to the sedation drug(s) or the IP.

7.5 Imaging Procedures

At each site, the same commercially available echocardiographic equipment and transducers will be used for all subjects. Subjects will be examined in either the supine or lateral decubitus position. The transmit power (≤ 0.8 MI) and the gain setting will be adjusted at the beginning of each procedure to obtain optimal endocardial visualization. Both settings must be kept constant throughout each subject's evaluation. Every effort must be made to keep the optimal transducer position for standard views. At each site, image acquisitions can be performed by the same sonographer throughout the study.

Prior to administration of IP, further evaluation for intracardiac shunt will be demonstrated with agitated saline study to assess the interatrial septum. If no evidence of intracardiac shunt is confirmed by the pediatric cardiologist, the subject will further undergo CEUS.

A pre-injection (baseline) UEUS with the standard apical 4, 2, and 3 views with harmonic imaging will be performed. Contrast-enhanced echocardiography will be performed with administration of the IP. A recording of 2D transthoracic harmonic echocardiography images will be performed from 30 seconds prior to injection of the IP and continued until all images are acquired. For CEUS images, the apical 4-chamber view will be acquired first followed by the apical 2- and 3-chamber views.

Both the UEUS and CEUS examinations must be identified by subject number and stored as DICOM clips for transfer to the central imaging lab according to the instructions provided in the Imaging Manual. The investigational sites are also required to maintain a copy of the subject's examination as a record of the study.

7.6 Pharmacokinetic Evaluation

A subset of subjects at one or two sites will undergo additional blood sampling for the determination of SF₆ concentration in blood. A total of 6 subjects (3 males and 3 females) age 9 and up to 12 years of age, and 6 subjects (3 males and 3 females) in the age >12 and up to and

[figure not shown]
including 17 years will have additional blood draws of 1 mL each immediately pre-dose, and at 1, 2, 3, 5, 10 and 15 minutes post-dose for the purposes of analyzing SF₆ concentration in blood. Blood samples will be taken from the arm contralateral to that used for the injection of LUMASON and analyzed by gas chromatography-mass spectrometry (GC-MS) or other acceptable method to obtain SF₆ concentration in blood. A designated laboratory will perform evaluations of SF₆.

7.7 Efficacy Evaluations

For all subjects, UEUS and CEUS images will be randomized and independently evaluated off-site by 3 blinded readers unaffiliated with the enrollment centers. No on-site evaluation of efficacy will be performed for this study.

From the apical 4-chamber, apical 2-chamber and apical long (3-chamber) views, the heart will be divided into 17 segments according to the guidelines of the American Society of Echocardiography¹⁷ as seen in Figure 1.

Figure 1 Three echocardiographic apical views used in the study

EBD for each segment will be graded by each off-site reader as:

- 0 = Inadequate (endocardial border not visible)
- +1 = Sufficient (endocardial border barely visible)
- +2 = Good (endocardial border clearly visible).

A separate off-site methodology document will be prepared and will contain the details regarding how the images will be anonymized, randomized and presented to the readers. No clinical information will be provided to the readers.

Both the UEUS and CEUS examinations must be identified by subject study identification number and stored as DICOM clips for transfer to the central imaging lab according to the instructions provided. Under Good Clinical Practices guidelines, the investigational sites are also required to maintain the subject's examination as a record of the study.

The timing of LV EBD assessment should start when LUMASON reaches from the apex to the mitral valve plane level.

The degree of LV opacification following injection will be graded according to the following 4-point rating scale:

- 0 = none, i.e., no visible contrast within the left ventricular cavity
- +1 = faint, i.e., weak or trace effect of contrast within the left ventricle
- +2 = non-homogeneous, i.e., some areas of the left ventricle fully opacified but without a time when the whole cavity is filled with contrast to the same high intensity
- +3 = complete, homogeneous and high intensity effect.

Useful appearance of contrast within the left ventricle including ventricular opacification rating of +2 (non-homogeneous) or +3 (complete and homogeneous) will be considered as adequate LV opacification.

8 Reporting Safety Information

The Investigator is responsible for the detection, documentation and reporting of adverse events.

Adverse event (AE) collection begins when a subject signs the Informed Consent and continues through the follow-up period defined in the Section 7.4.4.1 “Adverse Events” of the protocol. In addition, an investigator should report any serious AEs that occur after this time period that he/she believes may be related to the IP.

Any untoward medical occurrence that occurs from the time of signed Informed Consent to the time immediately prior to investigational product administration will be tabulated in the Clinical Trial Report as a “pre dose event.”

8.1 Adverse Events

8.1.1 Definitions

An AE is any untoward medical occurrence in a subject or a clinical trial subject administered a medicinal product and which does not necessarily have to have a causal relationship with the use of the product.

Any AE that occurs after the follow-up period defined in the protocol is not required to be collected in the AE section of the CRF.

An existing condition, which is detected by the diagnostic procedure conducted to test the efficacy of an investigational contrast agent, is not considered an AE.

Symptoms or medically significant laboratory or instrumental (e.g., electrocardiographic) abnormalities of a pre-existing condition, such as cancer or other disease, should not be considered an AE. However, new symptoms and laboratory or instrumental abnormalities, as well as worsening of pre-existing ones are considered AEs.

A serious adverse event (SAE) is any untoward medical occurrence that at any dose:

- results in death,
- is life-threatening (i.e. the subject was at risk of death at the time of the event/reaction; it does not refer to an event/reaction which hypothetically might have caused death if it were more severe),
- requires inpatient hospitalization or prolongation of existing hospitalization,
- results in persistent or significant disability/incapacity (where disability is defined as a permanent or substantial disruption of ability to carry out normal life functions, either reported or defined as per clinical judgment),

- is a congenital anomaly/birth defect,
- is an important medical event that may not result in death, be life-threatening, or require hospitalization but may be considered serious when, based upon appropriate medical judgment, it may jeopardize the subject and may require medical or surgical intervention to prevent any of the outcomes listed in the definition above. Examples of such events include allergic bronchospasm requiring intensive treatment in an emergency room or at home, and blood dyscrasias or convulsions that do not result in hospitalization, or development of drug dependency or drug abuse.

Any suspected transmission via a medicinal product of an infectious agent is also considered an SAE.

A non-serious AE is any AE that does not meet the criteria listed above for a SAE.

The reference safety document will be the same for the whole clinical trial.

An unexpected AE is one where the nature, severity, specificity or outcome is not consistent with the applicable product reference document.

In particular, the Sponsor will determine the expectedness of the AEs reported during this clinical trial according to the following reference document(s):

LUMASON: latest version of the Investigator's Brochure (IB). This will be provided as a separate document.

If an updated version of the reference safety document becomes available during the conduction of the study and before the last subject out, the Sponsor will provide the new version to all investigators. The new version will become the reference safety document for assessing the expectedness of AEs'.

An AE with fatal outcome should be considered unexpected unless the reference safety document specifically states that the event might be associated with a fatal outcome.

When it is uncertain whether an AE is expected, the AE should be treated as unexpected.

Upon notification of a serious AE, the Sponsor reviews all of the information provided by the Investigator and will urgently seek additional information when needed. The Sponsor will determine expectedness of the serious AE according to the latest version of the IB.

Reporting of serious AEs to the FDA will be done by the Sponsor according to the applicable and current Code of Federal Regulations (CFR). Additionally, any unexpected related serious adverse events will be reported to the investigators and Institutional Review Boards (IRBs) participating in the study as required by the applicable FDA CFR.

Whenever a serious AE is reported which is considered to be related to IP and unexpected based on the current IB, in addition to reporting to FDA, IRBs/Ethics Committees and Investigators as stated above, the Sponsor will review all available safety data to determine whether or not the study should be placed on hold and/or additional urgent safety measures added to the protocol. Any action taken in response to a safety concern will be communicated to FDA.

8.1.2 Expedited Reporting a Serious Adverse Event to Sponsor

The Investigator must report all serious adverse events **within 24 hours**, by telephone or by fax, to both the Drug Safety group and the Clinical Manager of the Sponsor as listed in Table D.

A Serious Adverse Event Report (SAER), see (Appendix C) must be completed by the Investigator and faxed to the Sponsor (both the Drug Safety group and the Clinical Manager) within 3 calendar days after the Investigator first became aware of the serious event. The top two copies of the completed SAER should also be sent to the Sponsor by traceable mail. The bottom copy remains on-site with the CRF.

In case of death, a comprehensive narrative report of the case should be prepared by the Investigator and sent to both the Drug Safety group and the Clinical Manager of the Sponsor by traceable mail together with the SAER, with a copy retained on-site with the CRF. If an autopsy is performed, a copy of the autopsy report should be actively sought by the Investigator and sent to the Sponsor as soon as available with a copy retained on-site with the CRF.

A follow-up SAER should be filled in by the Investigator if important follow-up information (e.g., diagnosis, outcome, causality assessment, results of specific investigations) becomes available after submission of the initial SAER. The follow-up SAER should be sent to the Sponsor in the same manner and following the same timeline as described for the initial.

If the Investigator becomes aware of any serious adverse events within the follow-up window established in the protocol following investigational product administration, they will be reported to both the Drug Safety group and the Clinical Manager of the Sponsor as described above.

If outside the follow-up window established in the protocol, any serious adverse events are reported to the Investigator, which he/she believes are related to the administration of the IP it is the Investigator's responsibility to report this serious adverse event to both the Drug Safety group and the Clinical Manager of the Sponsor. Such serious adverse events will be reported using a SAER or any other way chosen by the Investigator. Do not use the CRF.

The names, telephone, fax numbers, and email address of the contact persons are given below in Table D:

Table D: Adverse Events Reporting – Sponsor Contact Personnel

Name/Title	Office Telephone Number	Alternate Telephone Number	Fax Number / E-mail
North America			

8.1.3 Breaking the study blind

This is an open-label, non-randomized study

8.1.4 Data Collection

The Investigator will collect adverse events through non-leading questions and examination of the subjects.

For each event, record the following information in the Adverse Event section of the Case Report Form:

- **Classification of the Event:** Classify the event as either serious or non-serious (see definitions in Section 8.1.1).
- **Description of Signs or Symptoms:** Whenever possible, record a specific diagnosis for the event. If a diagnosis cannot be made, then record each sign or symptom separately. If multiple episodes of an event occur, separated by an appropriate time interval to justify considering the subsequent episodes as a repeat occurrence, record each episode separately on the Case Report Form. Indicate if the event is local (i.e., occurring at the site of administration). For serious AEs only: provide a detailed chronological description of the clinical course of the event(s) and of all relevant signs and symptoms.
- **Onset Date and Time:** Record the date and time the event started. If a change from pre dose in a laboratory test is reported as an adverse event, record the start date as the date of collection of the first lab sample that shows the change.
- **Stop Date and Time:** Record the date and time the event resolved. If a change from pre dose in a laboratory test is reported as an adverse event, record the stop date as the date of collection of the first post dose sample that shows a return to the pre dose level.
- **Intensity:**
 1. **Mild:** Event not resulting in disability/incapacity, which resolves without treatment.
 2. **Moderate:** Event not resulting in disability/incapacity, which requires treatment.
 3. **Severe:** Event resulting in temporary and/or mild disability/incapacity, which requires treatment.
- **Relationship to the IP:** Make every effort to determine the cause of each adverse event. Classify the correlation between the IP and the adverse event as follows:

1. Reasonable Possibility

The event falls into one of the two following categories:

- 1) a) The event follows a reasonable temporal sequence from administration of the IP;
AND
b) The event follows a known response pattern to the IP but could have been produced by any of the following features:
 - the subject's clinical state, or
 - other therapy administered, or
 - the diagnostic/interventional procedure;OR
c) The event cannot be reasonably explained by any of the following features:
 - the subject's clinical state, or
 - other therapy administered, or
 - the diagnostic/interventional procedure;OR
d) There is evidence of partial or complete disappearance of the event after withdrawal of the product (positive dechallenge).
- 2) The report of the event contains:
 - a) conflicting data
AND/OR
 - b) dubious or insufficient/poor evidence

2. No reasonable Possibility

The event is either a pre dose event or is definitely due to causes separate from the administration of the IP, i.e.,

- documented pre-existing condition
- technical and manual procedural problems
- concomitant medication
- the subject's clinical state
- the event is judged as not related and does not fall under either of the categories for "reasonable possibility"
- erroneous administration of treatment

- Action Taken:
 0. None
 1. Change in the investigational product administration (including brief interruption of administration of total dose and early termination of administration, i.e., dose reduction)
 2. Drug treatment required (a medication was prescribed or changed; record in the Concomitant Medication section of the Case Report Form)
 3. Non-drug treatment required (a non-drug treatment was prescribed or changed, record under “Comments” in the Adverse Event section of the Case Report Form)
 4. Hospitalization or prolonged hospitalization
 5. Diagnostic or clinical test(s) conducted (attach a copy of the results to the Case Report Form)
 6. Subject discontinued from the study
- Subject Outcome:
 1. Recovered without sequelae
 2. Recovered with sequelae (describe the sequelae under “Comments” in the Adverse Event section of the Case Report Form)
 3. Not Recovered, event on-going (follow the subject until a definite outcome can be determined. When follow-up data are collected, report follow-up information under “Comments” in the Adverse Event section of the Case Report Form; if the event is serious, fill in a follow-up Serious Adverse Event Report)
 4. Died (list primary cause of death under “Event Description” in the Adverse Event section of the Case Report Form; if available, attach a copy of the autopsy report to the Case Report Form and send a copy to Sponsor)
- Comments:

Provide other pertinent clinical information and observations, and the rationale for the provided causality under “Comments” in the Adverse Event section of the Case Report Form. For example, record predisposing or contributing conditions, such as previous history, concomitant diseases or medications, and/or procedural risks and explain the reasoning for attributing the event(s) to the cause chosen.

If the investigator states that there is no reasonable possibility that the event is related, he/she should provide details of an alternative explanation for the event.

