9.5 Safety Analysis

The safety data will be summarized for all subjects dosed. Summary tables, including change from UEUS to CEUS or clinically significant changes where applicable, will be presented for the following safety endpoints:

- Adverse Events
- Clinical Laboratory Evaluations
- Electrocardiograms
- Pulse Oximetry
- Vital Signs

All adverse events will be coded by MedDRA and summarized by system organ class and preferred term, by intensity and by causal relationship to the investigational product.

Only those occurrences which occur from the start of IP administration through the follow-up period defined in the protocol will be tabulated in the Clinical Trial Report as “adverse events” See Section 8.1.1.

Physical examination results, concomitant medication data will be presented in the data listings.

Summary statistics will be presented for volume of investigational product administered.

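### The adverse event intensity scale in Section 8.1.4 is not exhaustive and its top grade is capped too low, so the by-intensity tables can leave the gravest events ungraded or under-graded

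*Combined protocol and SAP*

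**What the plan says.** Section 8.1.4 (Data Collection) opens its list of items with the instruction "For each event, record the following information in the Adverse Event section of the Case Report Form", so the items apply to serious and non-serious events alike. Intensity is one of those items and has three grades:

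- Mild: "Event not resulting in disability/incapacity, which resolves without treatment"
- Moderate: "Event not resulting in disability/incapacity, which requires treatment"
- Severe: "Event resulting in temporary and/or mild disability/incapacity, which requires treatment"

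Seriousness is a separate item in the same list and refers back to Section 8.1.1. That section lists death, a life-threatening event, and an event that "results in persistent or significant disability/incapacity" as distinct criteria for a serious adverse event. Outcome is also a separate item, with its own codes for death and for an event still ongoing.

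Section 9.5 commits to summarising all coded adverse events "by intensity and by causal relationship to the investigational product". No other section of the combined protocol and SAP adds a further intensity grade or says how to handle an event that fits none.

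**The concern.** A scale applied to every event should give each event exactly one grade, and the worst events should land in the highest one. This scale classifies by two features only: whether the event disabled the subject, and whether treatment was needed. The top grade then covers only limited disability that was also treated. An investigator faced with a death, or with lasting and substantial disability, must leave the field blank or choose a grade whose definition is not met. Sites may make that choice differently.

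What is at stake is the by-intensity table in a paediatric study that has safety as a secondary objective (Section 4). Section 7.4.4.6 provides for subjects with pulmonary hypertension or unstable cardiopulmonary conditions, so grave events are foreseeable even if rare. Applied as written, the Severe row could read zero although such an event had occurred.

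**Working it through.** No stated figure in the plan depends on this scale, so there is nothing to reproduce. The check is one of coverage: cross the two features that the scale uses, and see which combinations receive a grade.

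| Disability or incapacity resulting | Treatment | Grade under Section 8.1.4 |
|---|---|---|
| None | Not required, event resolves | Mild |
| None | Not required, event does not resolve | None applies |
| None | Required | Moderate |
| Temporary, or mild, or both | Required | Severe |
| Temporary, or mild, or both | Not required, event resolves | None applies |
| Permanent and more than mild | Either | None applies |
| Death | Either | None applies |

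Three of the seven rows have a grade and four do not. Notes on individual rows:

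1. **Unresolved, untreated, non-disabling.** Mild needs resolution and Moderate needs treatment, so neither fits. The outcome codes in Section 8.1.4 include an ongoing event, and Section 7.4.4.1 ends routine monitoring at 72 hours, so the plan itself expects unresolved events.
2. **Severe.** Because its wording joins temporary and mild with and/or, the grade takes in disability that is substantial but temporary and disability that is lasting but mild, provided treatment was required. Among treated disabling events, only disability that is both permanent and more than mild falls outside.
3. **Disability resolving untreated.** Section 8.1.1 gives convulsions that do not lead to hospital admission as an example of an important medical event. A self-limiting convulsion that briefly incapacitates the subject is too disabling for Mild or Moderate and, being untreated, is not Severe.
4. **Death.** No grade is written for it. A literal reader could argue that death is not disability and so arrive at Moderate, which is hardly intended.

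**Life-threatening events.** Section 8.1.1 makes risk of death a seriousness criterion separate from disability, but the intensity scale does not use it. Two cases follow for a treated event:

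- Judged to have caused no disability or incapacity: Moderate, the same grade as any minor event that needed a medication.
- Judged to have caused even temporary incapacity: Severe.

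**Size.** Sections 5.1 and 9.8 give 92 enrolled to yield 73 evaluable, allowing 20% dropout (73 / 0.80 = 91.25, rounded up to 92). The safety population in Section 9.2 is everyone who received the product, and that number is not stated. Taking it to lie between 73 and 92:

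- 1 / 92 = 0.0109, or 1.1%
- 1 / 73 = 0.0137, or 1.4%

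This is the contribution of one event to the table. It says nothing about how likely such an event is, and the documents give no expected rate.

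**The case against.** The strongest reply is that intensity is only one of several fields. Seriousness, action taken and outcome are recorded for every event; death has an outcome code; sequelae must be described. Serious events need a chronological description and 24-hour notification, with a narrative report for deaths (Sections 8.1.2 and 8.1.4). The sponsor's review of whether to place the study on hold is triggered by seriousness, relatedness and unexpectedness (Section 8.1.1), not by the intensity grade. No hypothesis test uses intensity. On this view, the absence of a fatal grade is partly a design choice. All of this stands, and it limits the damage to the intensity variable and its tables. It does not make those tables right, because Section 9.5 promises them for all adverse events.

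Three stronger readings are tempting, and the documents do not support them:

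- A reader might infer that every life-threatening event reversed by treatment is graded Moderate. Temporary incapacity is enough for Severe, so Moderate applies only where no disability or incapacity resulted at all.
- A reader might infer that all disability meeting the serious-event criterion is ungraded. The and/or wording covers part of it when treatment is required.
- A reader might infer that the scale distorts expedited reporting, since Section 8.1.1 names severity among the features that make an event unexpected. Nothing there says that the intensity grade is used for that judgement.

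It can also be objected that placing life-threatening and fatal events in Severe brings seriousness into a scale that the protocol keeps separate. That is a fair point of design, but the present scale already rests on disability, which is itself a seriousness criterion when persistent or significant.

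**Conclusion.** The defect is real and narrow. As written, four kinds of event have no intensity grade, and a treated life-threatening event without disability or incapacity is graded only Moderate. The by-intensity tables could therefore leave the gravest events blank, place them in a grade whose definition they do not meet, or under-grade them. It would be wrong to conclude that these events would go unreported or that the safety data as a whole would be understated.

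The coverage result follows from the definitions alone. The size of 1.1% to 1.4% per event rests on the assumption that between 73 and 92 subjects are dosed; 92 is an enrolment figure and should not be read as the number dosed. The primary efficacy endpoints are unaffected. The change is worth making because it is cheap and a planned safety table depends on it.

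**What to change.** Reword the three grades in Section 8.1.4 so that they are exhaustive and non-overlapping, and reconcile them with Section 8.1.1:

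- **Severe:** any event resulting in disability or incapacity of any degree or duration, or that is life-threatening or fatal, whether or not treatment is required.
- **Moderate:** any other event requiring treatment.
- **Mild:** any other event not requiring treatment, whether or not it has resolved.

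Every row of the coverage table then has exactly one grade. The change affects data classification only: it needs no new assessments, has no effect on sample size, and leaves clinical management untouched.

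The cost is a one-time wording change to the protocol and the CRF instructions. One downside remains: brief, self-limited incapacity shares the top grade with much graver events. The separate seriousness and outcome fields still tell them apart.

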8.2 Special Situations

The Investigator must report all special situations **within 24 hours** by telephone or by fax using the form supplied by the Sponsor, to both the Drug Safety group and the Clinical Manager of the Sponsor as listed in Table D.

Special situations include but are not limited to the following: accidental overdose of IP, medication error with IP (such as administration of the wrong drug or wrong dose, wrong administration rate or wrong technique in drug usage process, administration via the wrong route, radiation under-dose, labeled drug-drug or drug-disease or drug-food interaction). In addition, any pregnancy of a subject or partner must be reported by the Investigator to the Sponsor within 24 hours using the Pregnancy Report form; any associated SAEs must be reported concurrently using the SAER.

In case urgent safety measures are taken during the conduct of the study these will be timely communicated by the Sponsor to the applicable regulatory authorities and also to concerned investigators and subjects.

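### Section 8.1.4 lists erroneous administration of an unspecified treatment as a non-IP cause, so an adverse event from an IP dosing error can be coded as unrelated

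*Combined protocol and SAP*

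**What the plan says.** Section 8.1.4 (Data Collection, relationship to the IP) offers two codes.

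- **Reasonable Possibility** has two routes. The first rests on timing after the IP together with features such as a known response pattern. The second takes in reports with conflicting data or "dubious or insufficient/poor evidence".
- **No reasonable Possibility** covers pre-dose events and events "definitely due to causes separate from the administration of the IP". An *i.e.* follows, and then a list of causes. The list includes "technical and manual procedural problems", concomitant medication and, as its last item, "erroneous administration of treatment".

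Under Comments, the same section says that an investigator who chooses the second code must justify it: "he/she should provide details of an alternative explanation for the event".

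Section 8.2 (Special Situations) requires reporting within 24 hours of, among other things, "accidental overdose of IP, medication error with IP (such as administration of the wrong drug or wrong dose". It does not say how the causality of a resulting adverse event is to be coded.

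Section 9.5 (Safety Analysis) summarises adverse events by system organ class and preferred term, "by intensity and by causal relationship to the investigational product". Section 8.1.1 describes a further sponsor step: "Whenever a serious AE is reported which is considered to be related to IP and unexpected based on the current IB", the sponsor reviews the safety data to decide whether the study should be put on hold.

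**The concern.** If a child receives the wrong volume of the IP and has an adverse event as a result, the event was caused by giving the IP. The last bullet nevertheless gives the investigator a listed reason for coding it as unrelated. *Treatment* is not defined, and the bullet has no exception for the IP.

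Obtaining safety data is a stated secondary objective (Section 4), and the tables by causal relationship are one of the main ways in which those data will be read. An event moved from the related to the unrelated column understates what the product did when it was given in error.

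**Working it through.** The point is definitional and the plan gives no figure to reproduce. The check sets the texts side by side.

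**1. Does the lead-in settle it?** Read strictly, it does: harm from a wrong IP dose is not separate from giving the IP. But the *i.e.* presents the bullets as being those separate causes. A coder who finds a bullet that fits has support in the text for using it. Lead-in and bullet pull in opposite directions.

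**2. Does the wording of the bullet settle it?** The word *treatment* (singular or plural) occurs 12 times in the supplied text:

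- Section 8.1.4: 7, one of them the bullet itself.
- Elsewhere: 5 (Introduction 1, the footnotes to Table B 1, Section 7.4.3 2, Section 8.1.1 1).
- 7 + 5 = 12, and 12 − 1 = 11 uses other than the bullet. All 11 mean therapy or medical care, which favours a non-IP reading.

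The noun *administration*, apart from the name of the regulatory agency, otherwise refers to the study product, including in the Section 8.2 description of medication error. That favours an IP reading. Concomitant medication and procedural problems also have bullets of their own, which leaves a purely non-IP reading less to cover. The wording does not decide the matter.

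**3. Does Reasonable Possibility take priority?** An event after an IP overdose can meet its timing and response-pattern criteria, or its second route if the evidence is poor. Only one item under No reasonable Possibility, the one for events judged not related, gives way expressly to the Reasonable Possibility criteria. The erroneous-administration bullet does not. The same event can fit both codes.

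**4. Does the duty to explain close the gap?** No. The bullet can itself be offered as the alternative explanation.

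**5. Does Section 8.2 close it?** No. It secures a report of the error but gives no causality rule.

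**6. What depends on the code?**

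| Step | Depends on the causality code? |
|---|---|
| Tables by causal relationship (9.5) | Yes |
| Notices to investigators and IRBs on unexpected related serious events (8.1.1) | Possibly; the section does not say whose assessment counts |
| Review of a possible study hold (8.1.1) | Possibly; same reason |
| Serious events within follow-up, to the sponsor in 24 hours (8.1.2) | No |
| Serious events after follow-up (8.1.2) | Not on the CRF code; it rests on the investigator's belief, and the CRF is not used |
| Special situations, to the sponsor in 24 hours (8.2) | No |
| Overall adverse event tabulation (9.5) | No |

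**7. Scale.** The rate of IP dosing errors is not given, so no expected number of events can be derived. The weight of one subject can be shown under an assumed denominator. Section 9.8 plans 92 enrolled to obtain 73 evaluable; the number dosed, which defines the safety population, is not fixed. If it lies between 73 and 92, one subject whose only related event is miscoded lowers the percentage with a related event by 1/92 = 1.1 to 1/73 = 1.4 percentage points. This is one subject over an assumed denominator, not an estimated effect.

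**The case against.** The strongest reply is that the lead-in governs every bullet. An item listed as an example of a separate cause is naturally read within that limit, the word *definitely* sets a high bar, and doubtful cases go to Reasonable Possibility. All 11 other uses of *treatment* point away from the IP, and the protocol usually names the product when it means it. The bullet also has a sensible non-IP meaning, such as an error in giving sedation. Overlap with other bullets proves little, since a pre-existing condition and the subject's clinical state overlap too. Section 7.4.4.7 adds a causality question that names the IP, although it sits under sedation and may apply only to sedated subjects.

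Much of this stands. It shows that coding the event as related is at least as good a reading, and that the text conflicts with itself. It does not show that the other reading is closed off: no sentence says that the bullet excludes the IP, and no precedence is stated.

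Two stronger conclusions might be inferred, and the documents support neither. The first is that the plan requires harm from dosing errors to be coded unrelated; the lead-in and the Reasonable Possibility criteria rule out a mandate. The second is that such harm would go unseen. The event is still collected and tabulated, serious events within follow-up and special situations reach the sponsor within 24 hours, the sponsor reviews each serious event (8.1.1), the causality rationale must be written down (8.1.4), and IP doses are listed by subject (9.4).

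**Conclusion.** The point holds as an internal conflict in Section 8.1.4. An adverse event from an IP overdose or medication error can be coded as unrelated, though it need not be. The one clear consequence is misclassification in the Section 9.5 tables by causal relationship. Two steps in Section 8.1.1 may also be affected, depending on whose assessment of relatedness is used there. The number of such events cannot be estimated. No efficacy endpoint or hypothesis test is involved. Severity is minor.

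The conclusion assumes that no form outside the supplied text (the CRF, the serious adverse event form or the special-situations form) already settles the reading. Those forms are not shown.

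**What to change.** Reconcile Section 8.1.4 with Section 8.2. Either delete the last bullet under No reasonable Possibility, or add the words *other than the IP* after *treatment*. An adverse event that follows an IP error is then assessed under the ordinary reasonable-possibility criteria, with no special rule in either direction.

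The cost is a change to one bullet. The downside is that a few more events may be counted as related.
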